7.5.3 Outcome

The outcome or the result of the untoward medical event / AE for a participant will be rated by the Investigator as;

Resolved: Fully recovered spontaneously or after medical or surgical intervention, i.e., the status is the same as the pre-study status.

^a If an investigational device gives an incorrect diagnosis, the patient might, for example, receive an unnecessary treatment and incur all the risks that accompany that treatment, or might be incorrectly diagnosed with a serious disease. In other cases, the patient might not receive an effective treatment (thereby missing out on the benefits that treatment would confer), or might not be diagnosed with the correct disease or condition.

Resolved with sequelae:	As a result of the event the participant has remaining significant symptoms or loss of function as, but not limited to, blindness, deafness, or paralysis. All untoward medical events that the participant has not fully recovered from and has significant remaining symptoms or loss of function should be handled as serious untoward medical events / SAEs.
Ongoing:	The status of the participant has not improved and the symptoms are unchanged.
Death	
Unknown:	The status of the participant is unknown. This term is to be used only when no other term applies, e.g., when the participant is lost to follow-up.

7.6 Capturing and Reporting of Untoward Medical Events / Adverse Events

Patients shall be asked about AEs at all visits (both site visits and telephone contacts). Questions for collecting AEs are specified in [Appendix 1, Section 4](#).

Adverse events can also be obtained from:

- Signs and symptoms from patient examinations,
- Laboratory values, or
- Spontaneous reports by subjects or their relatives.

All AEs and ADEs, will be captured in the section for AEs in the eCRF or in case of serious events in the section for SAEs, SADEs, or USADEs.

All events fulfilling the definition of untoward medical event will be captured and reported from the time when the participant signs the ICF and to the last visit in the study or until the participant has left the study. Untoward medical events may need follow-up after the last visit in the study before being rated as recovered or given a final status according to the definitions above.

7.7 Reporting of Serious Untoward Medical Events / Serious Adverse Events

The Investigator will report any SAE to the Sponsor authorized representative **immediately but not later than within 24 hours after awareness** that the event has occurred by completing the SAE eCRF pages.

Further reportable events, according to MEDDEV 2.7.3 rev. 3 have to be reported by the Sponsor/authorized representative to the National Competent Authority (NCA) where the event occurred using an SAE Report Table.

The following events are considered reportable:

- Any SAE
- Any device deficiency (See [Section 7.9](#)) that might have led to a SAE if:
 - suitable action had not been taken or
 - intervention had not been made or
 - if circumstances had been less fortunate

- New findings/updates in relation to already reported events.

The following timelines apply in case of:

- Serious public health threat:
 - Immediately, but not later than 2 calendar days after awareness by Sponsor.
- Death or unanticipated serious deterioration in state of health:
 - Immediately, but not later than 2 calendar days after awareness by Sponsor.
- Others:
 - Immediately, but not later than 7 calendar days after awareness by Sponsor.

7.8 Follow-up of Untoward Medical Events / Adverse Events

Any AE that is ongoing when the patient is withdrawn from the investigation should be followed-up until the AE is resolved or the Investigator decides that the AE is stable and needs no further follow-up. The last day for follow-up will be the study Day 35/42. AEs ongoing at study Day 35/42 shall be assessed as chronic or stable.

7.9 Device Deficiencies

A device deficiency will in this study be defined as an inadequacy of a medical device with respect to its identity, quality, durability, reliability, safety^a, or performance.

All device deficiencies related to the identity, quality, durability, reliability, safety or performance of an investigational medical device shall be documented in the eCRF. Device deficiencies include malfunctions, use errors, and inadequate labeling.

7.10 Tolerability

Based on AEs

7.11 Pregnancy

Subjects must be instructed to immediately inform the Investigator if any pregnancy should occur from the time of signing the informed consent form and 6 weeks onwards. Any confirmed study-subject pregnancy shall be reported by the Investigator on a Pregnancy Report Form immediately but not later than 24 hours of awareness and submitted to the Sponsor-authorized representative. Subjects becoming pregnant will be withdrawn from the study and followed until delivery, additional information on the infant will be collected until the infant is 1 month old. Adverse events in connection with the pregnancy, in the fetus, and in the infant up to 1 month of age will be reported. Any abortions (including elective abortions) together with abortion rationale should be reported and handled as SAEs; as well as any complications relating to the pregnancy, fetus, and infant fulfilling any criteria for seriousness. Procedures and timelines for AE/SAE reporting applies to reporting of AEs/SAEs in the pregnant subject, the fetus, and the infant.

^a Inadequacy of device safety refers to properties of the device that could have or have led to an AE.
Protocol Version 3.0, 24Oct2018

8 DATA HANDLING AND QUALITY ASSURANCE

8.1 Data Management

Data management based on GCP refers to the activities defined to achieve safe routines to efficiently enter patient information into a database, avoiding errors.

The data management routines include procedures for handling of CRF, eCRF and database set-up and management, data entry, data verification and validation (quality control of database), and documentation of the performed activities, including information of discrepancies in the process. The eCRF/ data entry screens, and the database/programs will be designed in accordance with the CIP and LINK standard operating procedure (SOP) system.

8.1.1 Data Collection

The clinical investigation data will be collected via eCRF completed by the Investigator or other qualified personnel at the site, and by the Clinical Trial Unit. Together these constitute a remote electronic data system, which complies with the associated requirements of EN ISO 14155:2011.

8.1.2 The Web-Based Case Report Form

Clinical data (including AEs and concomitant medications) will be entered into a 21 CFR Part 11-compliant eCRF (Viedoc4™). The eCRF includes password protection and internal quality checks, such as automatic range checks, to identify data that appear inconsistent, incomplete, or inaccurate. Clinical data will be entered directly from the source documents, unless the eCRF is considered source.

Authorized trial site personnel designated by the Investigator will complete data collection. Appropriate training and security measures will be completed with the Investigator and all authorized trial site personnel prior to get access to live version of the eCRF and any data being entered into the system for any trial patient.

The CRF specification provided in this CIP will be the basis for the set-up of the eCRF in Viedoc4™. However minor deviations might be necessary due to technical issues that cannot be foreseen during the CIP writing process.

8.1.3 The Entering of Data into the Electronic Case Report Form

The eCRFs should always reflect the latest observations on the patients participating in the trial. Therefore, the eCRFs should be completed as soon as possible during or after the patient's visit. The Investigator must verify that all data entries in the eCRFs are accurate and correct. If some assessments are not done, or if certain information is not available, not applicable or unknown, the Investigator should indicate this in the eCRF. The Investigator will be required to electronically sign off all collected data.

8.1.4 The Query Process

The Monitor will review the eCRFs and evaluate them for completeness and consistency. Each eCRF will be compared with the respective source documents to ensure that there are no discrepancies between critical data. All entries, corrections, and alterations are to be made by the Investigator or authorized designee. The Monitor cannot enter data in the eCRFs. Once

clinical data have been submitted to the central server via the eCRF, corrections to the data, made by the site personnel, will be audit trailed, meaning that the reason for change, the name of the person who made the change, together with date and time will be logged. Roles and rights of the site personnel responsible for entering clinical data into the eCRF will be determined in advance. If additional corrections are needed, the responsible Monitor or Data Manager will raise a query in the eCRF. The appropriate investigational personnel will answer the queries in the eCRF.

8.1.5 Signing of Data

Electronic CRF records will be automatically appended with the identification of the creator, by means of their unique User ID. Specified records will be electronically signed by the Investigator to document his/her review of the data and acknowledgement that the data are accurate. This will be facilitated by means of the Investigator's unique User ID and password. Date and time stamps will be added automatically at time of electronic signature.

8.1.6 Database Lock

All changes will be fully recorded in a protected audit trail, and a reason for the change will be required. Once all data have been entered, verified, and validated; and all queries are solved, medical coding approved, and SAE reconciliation performed; the database will be locked.

8.2 Patient Records and Source Data

The data may be recorded directly in the eCRF, which will then be considered as source data. The origin of source data in the investigation will be further specified in a separate document ("Origin of Source Data").

It is the responsibility of the Investigator to record essential information in the medical records in accordance with national regulations and requirements, including, but not limited to:

- Study code,
- Patient screening number and/or patient number,
- That informed consent for participating in the study was obtained, signed and dated by subjects,
- All visits during the investigation period,
- All AEs/ADEs SAEs/SADES, and
- Treatments and medications.

The Investigator is responsible for ensuring the accuracy, completeness, legibility, and timeliness of the data recorded in the CRFs.

8.3 Record Retention

The Investigator will retain copies of the records for a period of 15 years from the close-out visit. The Investigator must take measures to prevent accidental or premature destruction of these documents. In all cases, the Investigator must contact the Sponsor prior to disposing of any records related to the clinical investigation. Included in records to be retained are the

patients' medical records, signed CIP, copies of paper CRFs (if applicable), signed ICFs, IEC approval letters, product accountability records, correspondence concerning the clinical investigation, and any other documents to identify the patients (including the Patient Identification Log). The electronic data retention period is of at least 15 years. Archiving of data is performed according to industry standards such as in PDF/A format.

In addition, if the Investigator is no longer able to fulfill the role of Investigator (e.g. if he/she retires), a new Investigator will be appointed in consultation with the Sponsor.

8.4 Monitoring, Audits, and Inspections

During the investigation, the Monitor will have regular contacts with the investigational site. These contacts will include visits to confirm that the facilities remain adequate to specified standards and that the investigational team are carrying out the procedures stated in the CIP. All data must be accurately recorded in the eCRF and source data verified (comparison of eCRF data with the patient's medical records and other records at the investigational site). The eCRF and other records must be accessible during the visit.

The Monitor or other Sponsor personnel will be available between visits if the Investigator or other staff at the site needs information or advice.

Authorized representatives of the Sponsor or RA may visit the site to perform audits or inspections, including source data verification.

8.5 Training of Staff

A delegation log will be completed for each investigational site team member to indicate which activities the Investigator has authorized them to perform. This must be updated prior to a new or existing team member undertaking any new responsibility.

The Investigator will ensure that appropriate training relevant to the clinical investigation is given to the medical, nursing and other staff involved and that new information of relevance to the performance of this clinical investigation is forwarded to the staff involved.

9 STATISTICAL METHODS AND PLANNED ANALYSIS

The statistical planning, analysis and reporting work will follow LINK SOP system. All analyses described below will be performed using SAS Version 9.4.⁴⁶

For continuous data, number of missing and non-missing records, mean, standard deviation, median, 25th and 75th percentiles, minimum and maximum will be presented. All mean, median, confidence interval (CI), and standard deviation (SD) values will be formatted to one more decimal place than the measured value. Minimum and maximum values will be presented with the same number of decimal places as the measured value. Categorical data, including both nominal and ordered variables, as well as binary variables, will be presented by frequencies and percentages. Percentage values will be presented with 1 decimal place. In case of any hypothesis testing, p-values will be presented using a maximum of 4 decimal places.

The statistical analysis will be based on the observed data. However, if missing data, due to patient withdrawals or other reasons, or outliers, are considered to be an issue, measures will be taken in order to reduce bias or, in case bias is unavoidable, conservatively direct the bias.

Details on the presentation of descriptive statistics, analytical methods, and handling of statistical issues will be given in the statistical analysis plan (SAP).

9.1 Statistical Analysis

The clinical performance endpoints will be presented with the appropriate point estimate together with the 95% confidence interval. Any possible statistical testing will be performed using an overall significance level of 5%.

Although there are two co-primary endpoints, no adjustment of e.g. p-values or confidence intervals will be applied. This is for two reasons, the first being that the evaluation of the second co-primary endpoint (safety and tolerability) will only be based on descriptive statistics and data listings, and the second is that both co-primary endpoints have to show favorable results. For all other statistical analyses of the secondary endpoints, no adjustment due to multiple testing will be performed.

Statistical analysis will be based on all data, however, results will also be presented by site.

If the stated assumptions that the statistical evaluation is built upon can be questioned, suitable alternative methods may be applied. For example, a 95% confidence interval based on a non-parametric method may be applied if assumption of data belonging to the normal distribution seems not to hold. This, together with further details on the statistical analysis and identification of any possible exploratory or subgroup analysis, will be given in the SAP.

Sensitivity analyses may be performed to evaluate the robustness of the results.

Any deviations or changes to the study protocol specified statistical analyses will be documented and justified in the SAP and the Clinical Investigation Report (CIR).

9.1.1 Analysis Data Sets and Populations

The two different analysis datasets that will be considered for analysis is as below:

Full Analysis Set (FAS): This is the primary population and comprises all patients entering the study and having received at least 1 dose of study treatment. Analyses of clinical performance will be performed against this population.

Per Protocol (PP) Population - This will include all FAS patients without any major protocol deviation, i.e. patients who have completed the study and sufficiently complied with the study protocol, have available primary endpoint data and have received the study treatment according to protocol. The final definition of a major protocol deviation will be decided and defined at the clean file meeting. If a relevant number of patients are excluded from the PP population, then selected outputs will be provided for the PP population.

All safety analyses will be performed against the FAS. All patients included in the FAS will be accounted for, including those who did not complete the study along with the reasons for withdrawal.

Subject disposition table presenting the number and percentage of patients reaching each study milestone will be reported. The reasons for withdrawal from the study will be tabulated.

Patients who not qualify for the FAS population will be listed.

9.1.2 Demographic and other Baseline Characteristics

All demographic and other baseline data will be summarized descriptively. Demographic and baseline assessments will be presented descriptively using the principles stated in [Section 9](#) above.

Medical history will be coded according to MedDRA classification and will be presented by system organ class and preferred term as part of the baseline data.

Prior or concomitant medications will be coded using WHODD and summarized by ATC class.

Prior medications will be identified as those with a start date before Day 0 and will be presented as part of the baseline data. The concomitant medications will be defined as those with a start date equal to or after Day 0.

9.1.3 Exposure to Treatment

Treatment compliance data, see [Section 5.8](#), will be presented descriptively.

9.2 Primary and Secondary Endpoints Analysis

9.2.1 Primary Endpoints Analysis

- Clinical cure rate on Day 7 will be calculated and presented together with a one-sided 95 % confidence interval based on the exact binomial distribution.
- Safety and tolerability will be assessed according to [Section 9.2.3](#).

9.2.2 Secondary Endpoints Analysis

Below is the list of all secondary endpoints (highlighted in italics) and other related variables, together with information on variable types, followed by additional information on the planned statistical analysis and presentation of the endpoints. Note that the analyses of the secondary endpoints will be performed on different patient categories as described in [Section 2.2](#).

- a) CVVS score (can take integer values in the interval 0-18)
- a1) Vulvovaginal signs: erythema (can take integer values in the interval 0-3)
- a2) Vulvovaginal signs: edema (can take integer values in the interval 0-3)
- a3) Vulvovaginal signs: excoriation (can take integer values in the interval 0-3)
- a4) Sum of all vulvovaginal signs score (can take integer values in the interval 0-9)
- a5) Vulvovaginal symptoms: itching (can take integer values in the interval 0-3)
- a6) Vulvovaginal symptoms: burning (can take integer values in the interval 0-3)
- a7) Vulvovaginal symptoms: irritation (can take integer values in the interval 0-3)
- a8) Sum of all vulvovaginal symptoms score (can take integer values in the interval 0-9)
- b1) *Cure rate on Day 14* (based on values yes/no on the individual level, i.e. binary variable)
- b2) *Proportion endpoints* (based on values yes/no on the individual level, i.e. binary variables)
- c) *Change in CVVS score* (can take values from -18 to +14)
- d) *Change in sum of all vulvovaginal symptoms score* (can take values from -9 to +8)
- e) *Recurrence rates* (based on values recurrence=yes/no on the individual level, i.e. a binary variable)

f) *Usability, measured by patient questionnaire* (the questionnaire contains 4 specific yes/no (i.e. binary) variables, and a 5th question, “How do you generally regard the treatment?”, rated on a 1-10 integer scale).

In summary, the secondary endpoints:

- b1), b2), e), and the first 4 questions in f) are considered as binary variables
- c),d), and the 5th question in f) are considered as continuous variables

The binary endpoints categorized as b1), b2), and e) above, will be calculated and presented together with a two-sided 95 % confidence interval based on the exact binomial distribution.

Two-sided 95% confidence intervals will be presented for endpoints c), and d) using a parametric method assuming normally distributed data, i.e. arithmetic mean will be presented together with the 95% confidence limits.

Further, all study endpoints (primary, secondary, and exploratory), as well as the related variables specified in the list above, will be presented descriptively.

9.2.3 Tolerability and Safety Analysis

As part of the local tolerability and safety assessments, the following will be evaluated:

- Tolerability,
- Adverse events and SAEs, and
- Rate of withdrawals from the study and/or the study treatment.

9.2.3.1 Local Tolerability

Based on AEs

9.2.3.2 Adverse Events

The AEs will be presented descriptively by means of frequency and percentages to evaluate both the rate of incidence and event occurrence among the different treatment groups. The descriptive tables will be presented with respect to intensity, seriousness, and relationship to the treatment.

9.3 Sample Size Determination

Assuming the true cure rate is equal to 70 %, 22 patients are needed to obtain 90 % chance (90 % power) to show that the one-sided 95 % CI for the observed cure rate is above 40 %. To compensate for a small number of non-evaluable patients, 24 patients will be included.

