For patients not receiving prolonged treatment

- Recurrence rate on Day 14 and Day 35, defined as the proportion of patients clinically cured on Day 7 and thereafter responding “yes” to a yes/no question from the patient questionnaire on whether the symptoms have recurred

For patients receiving prolonged treatment

- Proportion of patients receiving prolonged treatment
- Clinical cure rate on Day 14, defined as the absence of signs and symptoms of VVC in terms of having a CVVS score equal to or below 3
- Proportion of patients having a reduction in CVVS score on Day 14 compared to Day 0
- Change in the CVVS score from Day 0 to Day 14
- Proportion of patients having a reduction in the sum of the 3 vulvovaginal symptoms scores (itching, burning, and irritation) on Day 11, Day 14, Day 21, and Day 42, compared to Day 0
- Change in the sum of the 3 vulvovaginal symptoms scores (itching, burning, and irritation) from Day 0 to Day 11, Day 14, Day 21, and Day 42
- Recurrence rate on Day 21, and Day 42, defined as the proportion of patients clinically cured on Day 14 and thereafter responding “yes” to a yes/no question from the patient questionnaire on whether the symptoms have recurred
- Proportion of patients receiving prescription for fluconazole on Day 14

Exploratory endpoint variables:

All patients

- Effect on vaginal microbiome on Day 0 and Day 7
- Vaginal pH on Day 7

For patients not receiving prolonged treatment

- Effect on vaginal microbiome on Day 35

For patients receiving prolonged treatment

- Effect on vaginal microbiome on Day 14 and Day 42

Safety and Tolerability Endpoints:

See above, safety and tolerability, based on reported treatment-emergent AEs.

Statistical Methods:

Sample size (n=24) is based on having 90 % power to show that the one-sided 95 % confidence interval for the observed cure rate is above 40 %, assuming the true clinical cure rate, as defined in this study, to be equal to 70 % in this patient population.

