### 5.1 *Sample size*

Assuming the true cure rate is equal to 70 %, 22 patients are needed to obtain 90 % chance (90 % power) to show that the one-sided 95 % CI for the observed cure rate is above 40 %. To compensate for a small number of non-evaluable patients, 24 patients will be included.

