### 7.9.1 Primary endpoints

- Clinical performance endpoint: Clinical cure rate on Day 7 will be calculated and presented together with a one-sided 95 % confidence interval based on the exact binomial distribution (Clopper-Pearson).
- Clinical safety endpoint: Safety and tolerability will be assessed according to [Section 7.10.2](#).

The primary clinical performance endpoint is the Clinical cure rate on Day 7, where clinical cure is defined as the absence of signs and symptoms of VVC in terms of having a composite vulvovaginal signs-and-symptoms (CVVS) score equal to or below 3, see [Section 3.1.1](#) above. The primary performance objective of the trial is to show that the Clinical cure rate is above 40 %, *i.e.* to show that the lower limit of the one-sided 95 % CI for the observed cure rate is above 40 %.

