#### Hypotheses for the primary clinical performance endpoint

Null hypothesis: Clinical cure rate is less than or equal to 40 %.

Alternative hypothesis (one-sided): Clinical cure rate is above 40 %.

The primary clinical safety endpoint, *i.e.* safety and tolerability based on reported treatment-emergent AEs, will be analysed descriptively only, see [Section 7.10.2](#) below, and will thus not be connected to any formal hypothesis testing.

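### The stated 90% power does not hold for the planned exact analysis: 22 patients give 81% and 24 give 85%

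*Protocol*

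**What the plan says.** Protocol section 9.3 starts from "Assuming the true cure rate is equal to 70"% and concludes that "22 patients are needed to obtain 90 % chance (90 % power) to show that the one-sided 95 % CI" for the cure rate is above 40%. It then adds two patients: "To compensate for a small number of non-evaluable patients, 24 patients will be included". SAP section 5.1 carries the same statement ("22 patients are needed to obtain 90 % chance (90 % power"). The Statistical Methods part of the protocol synopsis attaches the power to the larger number: "Sample size (n=24) is based on having 90 % power to show that the one-sided 95 % confidence interval" is above 40%. None of the three places names the formula behind the 22.

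The analysis itself is named. The protocol synopsis and section 9.2.1 call for an exact binomial interval, and SAP section 7.9.1 specifies a "one-sided 95 % confidence interval based on the exact binomial distribution (Clopper-Pearson"). The same SAP section sets the performance objective: "to show that the lower limit of the one-sided 95 % CI for the observed cure rate is above 40"%. The hypotheses that follow it make this a formal one-sided test ("Null hypothesis: Clinical cure rate is less than or equal to 40"%).

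**The concern.** The power statement and the analysis section refer to the same one-sided 95% interval, and the only version that either document defines for the primary endpoint is the exact one. With about two dozen patients the number of cures moves in whole steps, and the exact interval can need one more cure than a normal approximation does. A sample size taken from the approximation may then overstate the power of the test that will be run.

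At stake is the main design claim of a study with one formal hypothesis. Those who approve or fund the study read 90% power as a 10% chance of failure if the product works as assumed. Neither document gives the minimum number of cures, so a reader cannot see from the text where the line falls.

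**Working it through.** **Inputs.** True cure rate p1 = 0.70 (protocol 9.3, SAP 5.1). Threshold p0 = 0.40 (same sections; SAP 7.9.1 and its hypotheses). One-sided level 0.05, from the one-sided 95% interval. Evaluable patients: 22 by calculation, 24 enrolled (protocol 9.3). Interval: exact binomial (protocol 9.2.1), Clopper-Pearson (SAP 7.9.1).

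**Step 1: reproduce the plan's figure.** The one-sample normal approximation, with null and alternative variances, is

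n = [(z0.95·√(p0(1−p0)) + z0.90·√(p1(1−p1))) / (p1−p0)]²

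= [(1.645·√0.24 + 1.282·√0.21) / 0.30]²

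= [(0.8058 + 0.5873) / 0.30]² = 21.56, rounded up to 22.

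The power of the same approximation at n = 22 is Φ[(0.30·√22 − 0.8058)/√0.21] = Φ(1.312) = 90.5%. This matches the stated 22 patients and 90%.

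**Step 2: find the cut-off under the planned interval.** The Clopper-Pearson one-sided 95% lower limit for x cures out of n is the 5% quantile of Beta(x, n−x+1). Success needs this limit to exceed 0.40.

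- n = 22: 13 cures give 39.5% (fail); 14 give 43.9% (pass).
- n = 23: 13 cures give 37.5% (fail); 14 give 41.7% (pass).
- n = 24: 14 cures give 39.7% (fail); 15 give 43.7% (pass).

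At 22 and 24 the exact limit misses 40% by less than half a percentage point. Wald, Wilson, Jeffreys and mid-p limits all accept 13/22 and 14/24; the exact one does not. That is justified at the 5% level: P(X ≥ 13 | n = 22, p = 0.40) = 5.5% and P(X ≥ 14 | n = 24, p = 0.40) = 5.3%.

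**Step 3: exact power and type I error.** With c the minimum number of cures, power = P(X ≥ c | n, 0.70) and actual one-sided alpha = P(X ≥ c | n, 0.40).

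| Evaluable n | Minimum cures | Actual alpha | Power at 70% | Chance of missing |
|---|---|---|---|---|
| 22 | 14 | 2.15% | 81.4% | 18.6% |
| 23 | 14 | 3.49% | 88.0% | 12.0% |
| 24 | 15 | 2.17% | 84.7% | 15.3% |
| 25 | 15 | 3.44% | 90.2% | 9.8% |
| 26 | 16 | 2.17% | 87.5% | 12.5% |
| 27 | 16 | 3.37% | 92.0% | 8.0% |

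Exact power does not rise steadily with n. It first reaches 90% at 25, falls below at 26, and stays above from 27.

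**Step 4: the cure rate that would give 90%.** Solving P(X ≥ c | n, p) = 0.90 gives p = 73.6% for n = 22 and 72.3% for n = 24, against the assumed 70%.

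**The case against.** Five points can be made for the plan.

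- *The 22 is not a slip.* It is a correctly computed normal-approximation result, and protocol 9.3 names no method. This stands as a description of how the figure arose. The defect is a mismatch between the planning formula and the planned test, but the 90% is still untrue of that test.
- *The synopsis may only be shorthand.* It can be read as a compressed form of section 9.3, with 24 being 22 plus an allowance, so it is one mistake and not two. That is a fair reading. As written, though, the synopsis ties 90% to 24, and 24 does not deliver it either.
- *The consequence is limited.* Results such as 13/22 or 14/24 fail under the prespecified rule whatever power is printed, and the actual alpha at 22 and 24 is about 2.2% against 5%. This stands. The misstatement cannot create a false success or bias the estimate.
- *This is a feasibility study.* By the planned timetable in protocol section 12 the last visit was due in February 2019, and the SAP was finalised in January 2020. Correcting the text may therefore not affect recruitment. The documents still report a design property that the study did not have, and correcting it costs nothing.
- *The denominator is not settled.* SAP 7.1.1 makes all patients in the analysis set the default denominator, including those with missing data, while SAP 7.1.5 uses observed data without imputation. If all 24 count and two lack a Day 7 score, success needs 15 cures among the 22 observed, and power is P(X ≥ 15 | 22, 0.70) = 67.1%. This stands too. It makes the 90% claim harder to defend, and it shapes the correction.

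The clause in protocol 9.1 and SAP 7.9 that allows alternative methods when assumptions are in doubt does not help. Its example concerns normality, which the exact binomial interval does not assume.

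**Conclusion.** The concern holds. For the planned one-sided 95% Clopper-Pearson rule against 40%, at a true cure rate of 70%, power is below the stated 90% at each evaluable number from 22 to 24. The overstatement is 8.6 percentage points at 22 (90 − 81.4), 2.0 at 23 and 5.3 at 24. At 22 the risk of missing the objective is nearly twice the risk implied.

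These figures assume independent patients with a common cure rate of 70%, and a denominator equal to the number of patients with a Day 7 outcome. They show neither an inflated type I error nor an invalid design.

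**What to change.** In the protocol synopsis, protocol section 9.3 and SAP section 5.1, replace the 90% with the exact figures: 81% power with 22 evaluable patients, 88% with 23 and 85% with 24, for a true rate of 70% against 40%. State that these rest on the Clopper-Pearson lower limit, and say how the original 22 was obtained. Use the same n and power in all three places.

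Add the success rule as a count: at least 14 cures out of 22, 14 out of 23, or 15 out of 24. Before inserting it, reconcile SAP 7.1.1 with SAP 7.1.5 so that it is clear which patients form the denominator. A written count also removes any room to change the interval method after a near miss.

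The cost is wording only. The stated power becomes less favourable, and no change in enrolment is needed. Had 90% been a firm requirement, the smallest evaluable number reaching it under the exact rule is 25, and 27 is the first from which it is sustained.
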